## 3. Quality Performance Indicators

Multiple practice guidelines have been published for the management of AP (14–19). The recommendations in these guidelines are usually based on a systematic review of the relevant literature and the evidence on which is based on the available evidence, which is usually graded. Quality performance indicators will be drawn from these evidence-based recommendations for each of the nominated management domains that are relevant to the management of patients within the first 72 hours from admission to hospital. Any differences in the recommendations between the source guidelines will be resolved by discussion amongst the Scientific Advisory Group and consensus established for the QPIs.

The QPIs were developed for the following management domains: (Appendix D: Table 1 with guidelines)

**Table 1.** Quality Performance Indicators

	Domain	QPI	Ref*	Metrics
1	Diagnosis	All patients diagnosed within 12 hours of admission	IAP	RAC criteria for diagnosis: enzymes 3xUL, typical pain ± CT scan
2	Aetiology	All patients had tests for aetiology determined within 24 hours of admission	IAP	U/S for gallstones ETOH history with intake (units per week, timing of binge to pain) If both negative then lipids, IgG4, drugs
3	Severity (predicted)	All patients had prediction of severity on admission	IAP	N / Y, if yes method (drop-down of all options and other) Further drop-down bar will the give options for severity (mild, moderate, and severe)

4	Severity (actual)	All patients had actual severity determined at 48 hours	-	N / Y, if yes method (drop-down RAC, DBC and other) Further drop-down bar will the give options for severity (mild, moderate, and severe)
5	CT scan	Initial CT assessment performed after 72-96 hours if poor response to initial management or clinical deterioration, unless there is diagnostic uncertainty. Not required for severity prediction.	IAP	N / Y, if yes indication (drop-down with other)
6	Transfer	All patients with predicted or actual severe AP in the first 72 hours are discussed with specialist pancreas service.	Nice	N / Y Indication for transfer (drop-down)
7	Analgesia	All patients given narcotic analgesia within one hour of admission	-	Step-up or step-down approach? IV analgesia given on admission N / Y NSAIDS given to mild AP Analgesics prescribed

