8	Fluids	
 
All patients commenced on IV Hartmann's solution within one hour of admission to the emergency department by a clinician and at an initial rate of 5-10 ml /kg in response to hypovolemia until resuscitation goals reached.
 
Then a rate of 1-2 ml/kg/hour for patients not tolerating PO in the first 48 hours.
 
	IAP	IV fluids N / Y Time commenced from admission What initial fluid was given? Initial prescribed rate Initial received rate Average rate 2 nd 24 hours Average rate 3 rd 24 hours Fluid bolus given (# times and and timing) Volume / 24 hours over 72 hours?
9	Anticoagulation	All patients with predicted severe AP considered for or started on anticoagulation within 24 hours of admission	-	Anticoagulation N / Y Medication prescribed When started (hours from admission)
10	Antibiotics	Antibiotic prophylaxis not recommended for the prevention of infectious complications in AP	IAP	Antibiotic N / Y Antibiotic indication

11	Nutrition	
 
1. No patients made 'nil-by-mouth' and no food withheld unless there was a clear reason.
 
2. Offer EN to anyone with MSAP or SAP starting within 72 hrs.
 
3. PN avoided unless EN fails or is contraindicated
 
	NICE	Initial NBM N / Y From admission given trial of light diet. N / Y Initial NG or NJ? EN started within 72 hours if needed N / Y EN prescribed rate PN started if EN was not tolerated or contraindicated.
12	ERCP/ES	ERCP is indicated in patients with biliary pancreatitis and acute cholangitis within 48 hours of admission.	IAP	ERCP N / Y Indication: cholangitis or cholestasis When done? (hours)

\* Reference of guideline from which the QPI is primarily taken from

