## 4. Outcomes

### 4.1. Primary outcomes

- Proportion of patients that were managed in compliance with quality performance indicators overall

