## 5.5. Required data

Demographic details	
Age	Year of birth
Sex	Male/ Female/ Other
Ethnicity	European/ Pasifika/ Maori/ Asian/ Middle-Eastern/ Latin American/ African (MELAA)/ other ethnicity
Postcode	
Weight	kg
Height	cm
Smoking history	Current smoker /previous smoker /never smoker e-cigarette /cigarette
Admission details	
Date of first review by doctor/prescriber	Date (dd/mm/yyyy)  *From ED admission note
Time of first review by doctor/prescriber – as per admission note	24 hour clock time
Pancreatic enzymes at admission	Lipase/ Amylase/ Pancreatic amylase (tick one or more and give admission level and indicate what 3x upper limit is
Lipase/ amylase/ pancreatic amylase level	U/L
Epigastric pain confirmed on admission note	Yes/Non-epigastric abdominal pain/ No abdominal pain
Confirmation of AP diagnosis with imaging as per radiological report	MRI/ CT/ Abdominal USS
Charlson Comorbidity Index ( Appendix E )	Score out of 37
Aetiology	
Significant ETOH history investigated in first 72 hours	Yes - from medical history, Yes - ETOH blood test, No

Hypertriglyceridemia investigated in first 72 hours	Yes/No
Acute pancreatitis severity	
Predicted severity on admission as documented in clinical notes (72 hours)	Mild/ moderately severe/ severe
Method used to predict severity	Modified Glasgow/ Ransons'/ BISAP/ APACHE II/ SIRS/ CRP (>150)/ Other (please specify)/ Clinical judgement (no prediction tool)/ No prediction made.
Imaging	
CT assessment performed in the first 72 hours of presentation	Yes/ No
Indication for CT prior to 72 hours	Diagnostic uncertainty/ confirmation of severity based on clinical predictors of severe AP/ Failure to respond to conservative treatment or in the setting of clinical deterioration/ other (please specify)
Imaging of the gallbladder during admission	USS/ CT (gallstones seen on CT)/ MRI/ EUS/ prior imaging confirming gallstones/ previous cholecystectomy/ no imaging
Antibiotics	
Antibiotics administered in first 72 hours of presentation	Yes/ No
Indication for antibiotics	Cholangitis concomitant extrapancreatic infection/ prophylactic/ other – please state
Analgesia	
Simple analgesia (paracetamol/ NSAIDs) prescribed	Paracetamol/ NSAIDs/ Not charted
Simple analgesia frequency	regular/ PRN
Date simple analgesia first administered	Date (dd/mm/yyyy)

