Type of opioid prescribed (if any)	Codeine/ Morphine/ Fentanyl/ Tramadol/ Oxycodone/ Other (please specify)/ no opioids prescribed
Date opioid analgesia first administered	Date (dd/mm/yyyy)
Time opioid medication is administered to patient	24 hour clock
Route	PO/ IV
(If regular) daily dose	mg
(If PRN) total dose in first 72 hours	mg

(If yes) Date opioids first administered	Date (dd/mm/yyyy)
(If yes) Time opioid medication first administered as per drug chart?	24 hour clock
Further analgesic modalities	PCA/ ketamine/ local nerve blocks/ other (please specify)
Transfer to different hospital	
Patients with predicted severe disease discussed with specialised pancreas service ( Appendix B ) in first 72 hours from admission	Yes/ No/ not applicable
Patient transferred to a different hospital in the first 72 hours?	Yes/No
(If yes) Date of transfer	Yes/No
(If yes) Location transferred to	List of hospitals
(If yes) Reason for transfer to different hospital?	Severe disease/ requires ERCP/ requires interventional management of local complication/ other (free text)
ERCP	
Cholangitis in first 72 hours ( Appendix F )	Yes/ No
Cholestasis in first 72 hours (radiological + deranged LFTs)	Yes/ No
ERCP performed in the first 72 hours	Yes/ No
Fluid management*	
Baseline variables	
Bag 1	
Date of administration	Date (dd/mm/yyyy)
Time of administration	Time (24-hour)
Volume administered	Volume (ml)
How long does fluid run for?	Time (hours)
Type of fluid	0.9% Normal saline/ Hartmann's/ plasmalyte/ colloid/ 0.45 saline + dextrose/ 0.18 saline + dextrose/ other (please specify)
Further administration of intravenous fluid (IVF) in the first 3 days of admission? ( Appendix B )	Yes/no
Bag 2	
Date of administration	Date (dd/mm/yyyy)
Time of administration	Time (24-hour)

Volume administered	Volume (ml)
Time fluid is administered	Time (hours)
Type of fluid	0.9% Normal saline/ Hartmann's/ plasmalyte/ colloid/ other (please specify)
Further administration of intravenous fluid (IVF) in the first 2 days of admission?	Yes/no
Documented fluid review after 12 hours ( $\pm$ 4 hours)	Yes/no
Documented fluid review after 24 hours ( $\pm$ 4 hours)	Yes/no
Documented fluid review after 48 hours ( $\pm$ 4 hours)	Yes/no
Documented fluid review after 72 hours ( $\pm$ 4 hours)	Yes/no
Early Nutritional support	
On admission patient kept nil by mouth (NBM)	Yes/no

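### Table 1 and Section 5.5 disagree on the data behind the primary outcome: QPIs 2, 4 and 12 cannot be scored as worded, QPI 3 is ambiguous, and QPIs 1, 6 and 9 are scorable only in part

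*Protocol*

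**What the plan says.** Protocol Section 4.1 names one primary outcome: "Proportion of patients that were managed in compliance with quality performance indicators overall". Table 1 in Section 3 lists the twelve QPIs, most with a time limit, and a Metrics column saying what should be recorded for each. Section 5.5 is the list of required data.

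Three of the QPIs read:

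- QPI 12: "ERCP is indicated in patients with biliary pancreatitis and acute cholangitis within 48 hours of admission". Its metric asks when the ERCP was done, in hours.
- QPI 2: "All patients had tests for aetiology determined within 24 hours of admission".
- QPI 4: "All patients had actual severity determined at 48 hours". Its metric is a Yes/No item followed by method and grade.

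The matching fields in Section 5.5 read:

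- ERCP: "ERCP performed in the first 72 hours", Yes/No.
- Aetiology: "Significant ETOH history investigated in first 72 hours", a triglyceride item with the same 72-hour window, and "Imaging of the gallbladder during admission". None has a date or time.
- Actual severity at 48 hours: no field.

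Section 8 then plots QPI performance by hospital in funnel plots and relates compliance to clinical outcomes in mixed models.

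**The concern.** A QPI with a time limit can be scored only if the record shows whether the action fell inside that limit. If Section 5.5 is followed as written, an ERCP at 20 hours and one at 70 hours produce the same entry, although only the first meets QPI 12. The same happens to an alcohol history or triglyceride test at 10 hours and one at 60 hours under QPI 2.

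These fields feed the primary outcome, the hospital funnel plots and the comparison of compliant with non-compliant care. If an indeterminate Yes is counted as compliant, an early hospital and a late one look alike, and between-hospital variation is itself a secondary outcome. An analysis plan can set scoring rules, but it cannot supply times that were not recorded. The multiple imputation mentioned in Section 8 cannot rescue an item with no observed values, which is the position of QPI 4.

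**Working it through.** The protocol gives no expected compliance rate or sample size, so there is no figure to reproduce. The check sets Table 1 against Section 5.5.

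| QPI | Table 1 requires | Section 5.5 collects | Result |
|---|---|---|---|
| 12 ERCP | Within 48 h; metric in hours | Yes/No to 72 h, untimed | Not scorable as worded |
| 2 Aetiology | Within 24 h | Alcohol and triglycerides to 72 h; gallbladder imaging over the whole admission; all untimed | Not scorable as worded |
| 4 Actual severity | Determined at 48 h; Yes/No, method, grade | No field | Not scorable |
| 3 Predicted severity | On admission | Label refers both to admission and to 72 h; untimed | Ambiguous |
| 1 Diagnosis | Within 12 h | Enzymes and pain at admission; imaging modality without a time | Partial: indeterminate when the diagnosis depends on imaging |
| 6 Specialist discussion | Predicted or actual severe disease, 72 h | Predicted severe only, 72 h | Partial: window matches, scope does not |
| 9 Anticoagulation | Considered or started within 24 h; metric in hours from admission | 24 h and 48 h options for regular therapy; newly commenced therapy by type, with no start time | Partial |

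The tally is 3 not scorable, 1 ambiguous and 3 partial: 7 of 12 affected to some degree. The other five (5, 7, 8, 10, 11) are not part of this point.

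**What each answer tells the analyst.** For QPIs 2 and 12, and possibly 3, a No in a patient to whom the item applies shows non-compliance, since an action not done by 72 hours was not done by the earlier limit. A Yes leaves compliance unknown. For QPI 4 there is no answer of either kind: the result is missing, not inflated. The 30-day organ-failure items might let an analyst reconstruct severity, but not whether the clinical team determined it at 48 hours.

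**Effect on the overall outcome.** Section 4.1 does not say how the QPIs combine. If every applicable QPI must be met, no patient can be shown to be compliant, because QPI 4 applies to all patients and has no data. If the outcome is a share of QPIs met, QPI 4 drops out and at most 12 − 1 = 11 contribute.

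**Illustration of size (assumed inputs only).** Let d be the share recorded as done by 72 hours and f the fraction of those done after the QPI limit. If every Yes is counted as compliant, the QPI is overstated by d × f:

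- 0.50 × 0.10 = 5 percentage points
- 0.70 × 0.20 = 14 points (70% recorded, 56% true)
- 0.90 × 0.40 = 36 points

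For ERCP, f = (F(72) − F(48)) / F(72), where F is the distribution of time to ERCP. With exponential times and a median of 24 hours, f = (0.875 − 0.750) / 0.875 = 14.3%. Medians of 12 and 36 hours give 4.8% and 19.6%. Uniform times over 72 hours give 24/72 = 33%.

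This formula should not be carried over to gallbladder imaging. That field is not limited to 72 hours, and two of its answers (earlier imaging showing gallstones, earlier cholecystectomy) predate the admission and cannot be late.

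**The case against.** The strongest reply is that the fault is smaller than it looks. Table 1's Metrics column already asks for ERCP timing and for a 48-hour severity item, and the REDCap form is not shown, so the live form may contain them. The key linking hospital numbers to REDCap records is kept for 10 years, so sites could return to the charts. Both points are fair. They mean the protocol contradicts itself, not that the times are certainly lost, and that later repair would require chart re-abstraction at every site. Neither removes the need to reconcile the two lists, because Section 5.5 is the one headed as required data.

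Four stronger readings are tempting, and the documents do not support them.

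- *Six or more QPIs cannot be scored at all.* QPI 1 can be inferred when pain and enzymes both qualify at admission, since Appendix B requires two of three features. QPI 6 has the right window and lacks only the patients with actual severe disease. QPI 3's field does refer to admission and has an option for no prediction. QPI 9 has timed options for regular therapy.
- *Overall compliance is overstated.* The protocol states no rule that counts a 72-hour Yes as compliant. Upward error arises only under such a rule, for QPIs 2, 12 and possibly 3. QPI 4 would be missing, and QPI 9 could be understated because therapy considered but not started is not captured.
- *The clock starts in the wrong place because the form records "Time of first review by doctor/prescriber".* QPI 8 and Section 5.6 both describe admission to the emergency department by a clinician, which fits that field. QPIs 7 and 8 have a date and clock time at both ends.
- *The protocol avoids times on purpose.* It collects dates and times for opioids and fluids, and dates for interventions on collections.

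**Conclusion.** The point holds in limited form and should be settled before the form goes live, because it concerns the sole primary outcome. Three of twelve QPIs (2, 4, 12) cannot be scored as worded from Section 5.5, one (3) is ambiguous, and three (1, 6, 9) can be scored only in part. Counting every Yes as compliant would overstate QPIs 2 and 12, and possibly 3, and would blur differences between hospitals. By how much cannot be known from the documents: the 5 to 36 points and the ERCP percentages above are arithmetic on assumed inputs. The direction and size of the net effect on the overall outcome are unknown. The conclusion rests on Section 5.5 being the list that sites follow.

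**What to change.** Before the form goes live, bring Section 5.5 into line with Table 1:

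- add date and time for seven events: ERCP, gallbladder imaging, alcohol history, triglyceride test, documented severity prediction, diagnostic imaging, and newly started anticoagulation;
- add an item for actual severity determined at 48 hours (Yes/No, method, grade);
- extend the specialist-discussion item to cover actual as well as predicted severe disease.

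Where the authors prefer the window now on the form, the QPI and its field must be aligned in the text. Which window is clinically right is for them to decide.

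The form uses separate date and time fields, so the additions come to 7 × 2 + 3 = 17 entries, or roughly 15 to 20 depending on layout. They come from notes and charts already being read, and not all apply to every patient. Data entry will take longer, some times may not be charted, and reported compliance may be lower than it would be if every untimed Yes were accepted.

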### 4.2. Secondary outcomes

- Variation in compliance with QPIs between hospitals for each of the management domains
- Requirement for mechanical ventilation (invasive and non-invasive)
- Requirement for renal replacement therapy
- Requirement for inotropic or vasopressor support
- Intervention for a complication of AP
- Alive and discharged at 30-days

[figure not shown]

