Indication for NBM	for ultrasound scan/ for surgery/ for ERCP/ unknown reason/ other (please specify)
Patient tolerating PO oral intake (clear fluids) by 24 hours	Yes/no
Patient tolerating PO oral intake (clear fluids) by 48 hours	Yes/no
Patient tolerating PO oral intake (clear fluids) by 72 hours	Yes/no
Enteral feeding started in the first 72 hours?	Yes/no
Tolerating enteral feed	Yes/no
Type of Enteral feeding	NJ/NG
Rate of enteral feed	ml/hr
PN in the first 72 hours?	Yes/no
Rate of PN	ml/hr
Anticoagulation	
On regular anticoagulation therapy prior to admission	Warfarin/ dabigatran/ rivaroxaban/ other (please specify)/ Not on regular anticoagulation therapy
Regular anticoagulation continued on admission	Yes/No
(If yes) type of anticoagulation drug	warfarin/ dabigatran/ rivaroxaban/ other
Regular anticoagulation commenced on	Yes - at 24 hours/ Yes - at 48 hours/ No

admission	
Anticoagulation commenced on admission	Prophylactic-dose clexane/ treatment-dose clexane/ anticoagulation not started/ other (please specify)
Local complications in the days prior to the 30-day follow-up	
Necrotising pancreatitis ( Appendix B )	Yes/no
Acute necrotic collections (ANC)	Yes/no
Infected ANC	Yes/no
(If yes) intervention	Endoscopic/ percutaneous/ open necrosectomy
(if yes) date of intervention	Date (dd/mm/yyyy)
Acute pancreatic fluid collection (APFC)	Yes/no
Infected APFC	Yes/no
(if yes) intervention	Endoscopic/ percutaneous/ open necrosectomy
(if yes) date of intervention	Date (dd/mm/yyyy)
Portal/ splenic vein thrombosis	Yes/no
Other local complications	Pleuro-peritoneal fistula/ pleural effusion/ enteric fistula/ gastrointestinal bleeding/ pancreatic ascites/ arterial pseudoaneurysm/ other (free text)
Organ failure and other outcomes during the last 30-days follow-up	
Final aetiology	Alcoholic/ gallstone/ hypertriglyceridaemia/ others
Acute renal failure (as per RIFLE criteria - Appendix A )	Yes/no
Acute renal failure > 48 hours	Yes/no
ICU admission	Yes/no
(If yes) duration of ICU admission	day(s)
New renal dialysis required	Yes/no
(If yes) duration of dialysis	day(s)
New high-flow oxygen/ AIRVO requirement	Yes/no
Duration of high-flow/ AIRVO	days
Noninvasive ventilation required	Yes/no
(If yes) duration of noninvasive ventilation	days
Mechanical ventilation required	Yes/no

(If yes) duration of mechanical ventilation	day(s)
Inotropes required	Yes/no
(If yes) duration of inotropic support	day(s)

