Date of mortality (within 30 days of first admission)	Date (dd/mm/yyyy)/ not dead
Date of discharge	Date (dd/mm/yyyy)/ not discharged

*\* Fluid therapy data collection guide: If collaborators respond, 'yes' to the question 'further administration of IVF in first 72 hours of admission?' a further set of questions will arise for 'bag 2', 'bag 3' etc.*

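### The fields listed for interventions are narrower than the secondary outcome they must supply, so that outcome will be under-counted

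*Protocol*

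**What the plan says.** Section 4.2 of the protocol, like the Study Summary, lists "Intervention for a complication of AP" among the secondary outcomes. Neither place restricts which complications count.

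The data meant to supply it are in section 5.5, in the block on local complications up to the 30-day follow-up. Intervention appears there twice, each time as an if-yes row with a date. The first sits directly under the item on infected acute necrotic collection, the second directly under "Infected APFC". The choices are the same both times: "Endoscopic/ percutaneous/ open necrosectomy".

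The same block also records "Portal/ splenic vein thrombosis" as yes/no, and a list of other local complications: "Pleuro-peritoneal fistula/ pleural effusion/ enteric fistula/ gastrointestinal bleeding/ pancreatic ascites/ arterial pseudoaneurysm/ other (free text"). Neither has an intervention row.

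For "Alive and discharged at 30-days", also in section 4.2, section 5.5 has a date of death within 30 days of first admission (or not dead) and a "Date of discharge" (or not discharged).

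**The concern.** The outcome is defined broadly and collected narrowly. A patient who has a procedure for a bleeding pseudoaneurysm, a fistula or pancreatic ascites meets the outcome as worded, yet the list has nowhere to enter that procedure. At analysis this patient looks the same as one who had no intervention.

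The outcome feeds the secondary aims that relate compliance to clinical outcomes, and the mixed-effects logistic models in section 8. The error runs one way, because procedures are lost and none are invented. It also falls on the complicated patients, who supply the events. An analysis plan can choose how to define an outcome, but it cannot recover procedures that were never recorded.

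**Working it through.** The protocol states no expected rate, sample size or power for this outcome, so there is no figure to reproduce. The check traces the outcome to the fields in section 5.5.

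**1. Complication by complication**

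| Complication recorded in section 5.5 | Intervention row? |
|---|---|
| Infected necrotic collection | Yes, three choices |
| Infected fluid collection | Yes, the same three choices |
| Non-infected necrotic or fluid collection | No, if the condition attaches to the row directly above; yes, if it attaches to the presence of any collection |
| Portal or splenic vein thrombosis | No, on either reading |
| Fistula, effusion, bleeding, ascites, pseudoaneurysm, other | No, on either reading |

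By contrast, ventilation, dialysis and inotropes in the same section each have their own unconditional yes/no item.

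**2. Could another field fill the gap?**

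- The transfer block offers "requires interventional management of local complication" as a reason for transfer. That is an indication, limited to transfers in the first 72 hours. It does not show that a procedure was done.
- The ERCP item covers the first 72 hours only and is not tied to a complication.
- The free-text choice under other local complications asks for a complication, not for its treatment.

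None of these supplies the outcome.

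**3. Size, as an illustration only**

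Let p be the true proportion of patients with an intervention. Let s be the share of those patients whose only interventions were for something without a field. Then

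recorded rate = p × (1 − s).

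Both inputs are assumptions; the documents give neither. With p = 5%:

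- s = 10%: 5% × 0.90 = 4.5%
- s = 25%: 5% × 0.75 = 3.75%
- s = 50%: 5% × 0.50 = 2.5%

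If s is the same in compliant and non-compliant patients, the factor (1 − s) cancels from a ratio of risks. It still shrinks the risk difference and the number of events. If s differs between the groups or between hospitals, the comparison itself is distorted.

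**4. The discharge outcome**

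A patient recorded as not dead, with a discharge date by day 30, is a success. A patient with a date of death by day 30, or recorded as not discharged, is not. The outcome can therefore be derived. What is unstated is how to classify a patient who is discharged, readmitted and in hospital on day 30: section 5.5 has no readmission item, and no rule says which discharge counts.

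**The case against.** Four arguments can be made against the point.

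- **Section 5.5 is a list of required data, not the REDCap form.** The Study Timeline treats the form as a separate deliverable, and the list uses shorthand elsewhere. This stands in part. It would be unsafe to assert that the live form has no way to enter no procedure, or that hospitals will read a blank differently. But a form built from the list as written would carry the gap.
- **The if-yes condition may attach to any collection, not only an infected one.** Branching is not visible in the table. Row order favours infection, but the looser reading cannot be excluded. It restores only the non-infected collections.
- **Some procedures can be found by other routes.** Local leads keep a key that allows re-identification (section 5.3), so charts could be reopened. That is true, but it means a second round of collection for something the planned 30-day review could capture once.
- **These are secondary outcomes.** That is correct; the primary outcome, compliance with the quality indicators, is unaffected.

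A reader might also infer that the discharge outcome rests on a single date and is misclassified too, so that both outcomes are under-counted. The documents do not support this. A separate mortality date supplies the vital status, and the discharge item allows for patients not discharged. Any error from readmission would arise only if the outcome means status on day 30, and it would then over-count successes. Nor can the affected patients be counted: the protocol gives no readmission rate and no planned sample size.

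**Conclusion.** The point holds for one outcome. As listed, the fields in section 5.5 cannot supply the intervention outcome named in section 4.2, and following them would under-count it. On the loosest reading, the loss covers procedures for thrombosis, bleeding, pseudoaneurysm, fistula, ascites and effusion. On the natural reading it also covers non-infected collections. The direction is certain if the list is followed as written; the size is not known. The figures of 4.5%, 3.75% and 2.5% only show how the recorded rate moves under an assumed true rate of 5%.

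The discharge outcome needs only a clarification. It is derivable, but the protocol does not say whether readmission reverses discharge.

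**What to change.** In section 5.5, add one unconditional item to the 30-day review: whether any procedure was done for any complication of pancreatitis up to day 30 (yes/no). If yes, record the complication treated, the type (endoscopic, percutaneous, radiological, surgical, other) and the date. State that the secondary outcome is derived from this item. An explicit no also separates no procedure from missing data.

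For the discharge outcome, choose one of two routes. Either define it as alive with the index discharge by day 30, which needs no new data, or add a yes/no item on being in hospital on day 30, counting readmissions, and define the outcome from that item and the date of death.

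The information comes from the chart review already planned in section 5.6. The cost is a few REDCap fields and about a minute more per patient.

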### Secondary Aims:

- To measure the variation in compliance with QPIs between each hospital in AoNZ for each management domain for the management of AP during the first 72 hours after admission.
- To correlate compliance (overall and for each management domain) with QPIs and defined clinical outcomes stratified by AP severity.
- To compare clinical outcomes between compliant and non-compliant management of patients stratified by AP severity.

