#### *Exclusion Criteria*

- Age less than 16
- Chronic pancreatitis (*Appendix B*)
- Patients with suspected respiratory distress ( $SpO_2/FiO_2 \leq 315$ ) who did not have an arterial blood gas test done to confirm respiratory failure.
- Postoperative pancreatitis following upper gastrointestinal surgery (not including endoscopic retrograde cholangiopancreatography [ERCP])

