**Appendix A (i) - Revised Atlanta Classification of AP severity**

Severity	Definition
Mild acute pancreatitis	Absence of organ failure Absence of local complications
Moderately severe acute pancreatitis	1. Local complications AND/OR 2. Transient organ failure (<48 hours)
Severe acute pancreatitis	1. Persistent organ failure (>48 hours)

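### Actual severity has no field, and non-renal organ failure is recorded only as undated support in days, so Appendix A severity can only be approximated and the actual-severity denominators of QPI 6 and QPI 11.2 cannot be formed faithfully

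*Protocol*

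**What the plan says.** **Severity definition.** Protocol Appendix A(i) makes disease mild when there is neither organ failure nor a local complication. It is moderately severe with local complications and/or "Transient organ failure (<48 hours", and severe with "Persistent organ failure (>48 hours". No organ is singled out.

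**Data form.** Section 5.5 has a renal item, "Acute renal failure (as per RIFLE criteria", and a persistence item, "Acute renal failure > 48 hours". For lung and circulation it asks whether high-flow oxygen, non-invasive ventilation, mechanical ventilation or inotropes were needed, and for how many days. These items cover the 30-day follow-up and carry no onset date. Local complications are yes/no over the same period, and only interventions on infected collections are dated. Predicted severity is recorded with its method. No item asks for actual severity.

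**What uses severity.** The Table 1 metric for QPI 4 specifies a drop-down for the method and grade of actual severity. QPI 6 reads "All patients with predicted or actual severe AP in the first 72 hours are discussed with specialist pancreas service", but the matching item in section 5.5 concerns predicted severe disease only. The second part of QPI 11 reads "Offer EN to anyone with MSAP or SAP starting within 72 hrs". Secondary aims 2 and 3 are stratified by severity, for example "To compare clinical outcomes between compliant and non-compliant management of patients stratified by AP severity". Neither says whether predicted or actual severity is meant.

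**Eligibility.** Section 5.4 excludes patients with suspected respiratory distress "who did not have an arterial blood gas test done to confirm respiratory failure".

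**The concern.** The severity definition needs organ failure, its duration relative to 48 hours and, for indicators set at 72 hours, its timing. The form supplies failure and duration directly only for the kidney, and timing for no organ. The eligibility rule gives up patients so that respiratory failure is confirmed by blood gas, yet section 5.5 has no field for the result.

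QPI 6 and QPI 11 contribute to the primary outcome, overall compliance with the indicators. A patient wrongly left out of, or put into, one of these denominators is scored on an indicator that does not apply, or not scored on one that does. If the secondary aims use actual severity, the same patients fall in the wrong stratum.

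**Working it through.** The protocol states no figure to reproduce here. The check sets what is needed against what section 5.5 collects.

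| Needed | Collected in section 5.5 | Gap |
|---|---|---|
| Renal failure | Yes/no by RIFLE, plus a 48-hour flag | Onset date |
| Respiratory failure | Three kinds of support, in days | Failure item, definition, 48-hour flag, onset |
| Circulatory failure | Inotropes, in days | Failure item, definition, 48-hour flag, onset |
| Local complications | Yes/no over 30 days | Date first identified |
| Actual severity (QPI 4) | Nothing | Method and grade |
| Predicted severity | Grade and method | None |

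Respiratory failure managed without high-flow oxygen or ventilation leaves no organ-failure entry. Nor does hypotension without inotropes.

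**Days against the 48-hour cut.** No counting rule is given, so each of these is an assumption:

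- Rounded days: an entry of 2 covers 1.5 × 24 = 36 h to 2.5 × 24 = 60 h, which straddles the cut.
- Calendar dates touched: an entry of 2 covers anything up to 2 × 24 = 48 h. An entry of 3 covers just over 24 h to 3 × 24 = 72 h, which straddles the cut.
- Completed days: an entry of 2 covers 48 h to just under 72 h.

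Entries of 2 or 3 days are therefore unclear. An entry of 1 is below the cut, and 4 or more is above it, under all three rules. Even then, time on support is not the same as time in organ failure.

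**Timing against 72 hours.** For severe disease to be established by 72 hours, failure must begin by about 72 − 48 = 24 h after admission. Without onset dates, such a patient cannot be told from one whose organ failed later in the 30 days. For QPI 11.2 the action is due within 72 hours, so the sensible denominator is patients who are moderately severe or severe by then. Both routes into that group, organ failure and local complications, are undated.

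**Support as a stand-in for failure.** Section 4.2 lists mechanical ventilation, renal replacement and inotropic or vasopressor support as secondary outcomes. If the strata of aims 2 and 3 were built from those items, the mild stratum would contain none of these events by construction. The strata would be defined by the outcomes compared within them.

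**The case against.** **The form holds more than a renal flag.** A reader might infer that Appendix A severity cannot be derived at all. That goes too far. Support and its duration are recorded, and local complications alone make disease moderately severe, so an approximation over 30 days is available. This stands.

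**The aims may not need actual severity.** A reader might also infer that aims 2 and 3 fail. They say only that results are stratified by severity, without citing Appendix A, and the severity block of section 5.5 holds predicted severity. The aims could be run on that variable. This stands, but the protocol does not make the choice.

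**QPI 6 and QPI 11 are hit only in part.** Predicted severe disease can be identified. The QPI 6 patients at risk of being missed are those with failure starting in about the first 24 hours who were not predicted severe. In QPI 11, only the second of three parts depends on severity grade. Both points stand and limit the size.

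**No patient count is possible.** A reader might want the number graded too mild. The Background gives 20% with moderate or severe disease. The documents give no cohort size, no organ-failure rate by system, and no share managed without recorded support. Some such patients would in any case leave the mild group through a local complication, renal failure or other support.

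**A definition or field may exist elsewhere.** Reference 22, on pulse oximetry in respiratory distress, is not cited in the text available, so a respiratory definition may stand in a part of the appendices not seen. The REDCap form may also hold more than section 5.5 lists. Either is quickly checked. A definition alone would supply neither the 48-hour flag nor the onset date.

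**Conclusion.** The point holds in this limited form. Section 5.5 does not carry the actual-severity item that Table 1 specifies for QPI 4. Outside the kidney, organ failure appears only as undated support in days, and local complications are undated as well. Appendix A severity can be approximated, not derived faithfully.

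Three of twelve indicators are touched. QPI 4 lacks its own field, QPI 6 loses the actual-severe part of its denominator, and QPI 11 loses a faithful 72-hour denominator for one of its three parts. The secondary aims are affected only if actual severity is intended. In that case a support-based proxy would also make the comparison partly circular.

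This rests on section 5.5 being the full field list and on reading QPI 11.2 as applying to severity reached by 72 hours. It does not rest on any assumed event rate. It should be corrected in the protocol, because later analysis cannot supply the missing data.

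**What to change.** In section 5.5:

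- Add the actual-severity item that Table 1 names for QPI 4, with method and grade.
- Add respiratory failure and circulatory failure as yes/no items, each with a stated definition, a flag for more than 48 hours, and onset date and time. Add onset date and time for renal failure.
- Add the date on which each local complication was first identified.
- Record organ support as start and stop times instead of days.
- Align the QPI 6 form item with the indicator, so that it covers predicted or actual severe disease.

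In the analysis text:

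- Form the QPI 6 and QPI 11.2 denominators from severity status reached by 72 hours. Onset within 72 hours combined with the 48-hour flag is not equivalent: it admits severity established only by 72 + 48 = 120 h.
- State whether predicted or actual severity stratifies secondary aims 2 and 3. If actual, acknowledge the overlap with the organ-support outcomes. Better fields reduce that overlap but do not remove it, since support is given for organ failure.

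The cost is a slightly longer form. The charts are already reviewed over the first 72 hours and at 30 days under section 5.6, and patient care does not change. Section 5.3 places the first collection at or within 48 hours, so the two sections need reconciling for a 72-hour status to be recorded.
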